Pilot data from our currently funded FRQS project focusing on cognition and AMD indicate correlations between sensory and cognitive variables in the expected directions insofar as individuals with faster reading speeds demonstrated better scores on the Montreal Cognitive Assessment^{57,58}. Given the information reviewed above, the logical direction for our investigation into the functional connection between LV and cognition is to examine the possible effects of reading rehabilitation on the cognitive abilities of LV patients over time. In order to dis-entangle the effects of visual and cognitive impairments in older adults, members of this research team have adapted cognitive tests so they can be administered to individuals with low vision^{59,60}. In parallel, we are also in the process of developing a vision-screening test that can be administered to individuals with various levels of cognitive impairment^{61,62}. This investigation will guide our future research efforts into the improvement of service provision in LV rehabilitation for the purpose of increasing the independence and health of older adults living with LV.

[figure not shown]
The objectives are to:

- Evaluate cognitive functioning and memory before, and 6 and 12 months after low vision reading rehabilitation using magnification in AMD patients, compared to those with dual (vision and hearing) impairments, and age-matched controls
- Correlate participant characteristics with all cognitive outcome variables in order to identify potential mediators, moderators or confounders

Hypotheses:

- Measures of reading effort (self-report and objective reading speed) will be statistically significantly reduced after participants have received strategies and tools to facilitate reading.
- Measures of reading behaviour will be negatively correlated with measures of reading effort (e.g., participants who report less effort will read a greater amount, more frequently and for longer)
- Individuals who demonstrate reduced reading effort and improved reading behaviour will demonstrate improved scores on cognitive tests after 6 months of having received rehabilitation strategies and tools, compared to those whose reading effort remains high or whose reading behaviour remains unchanged. These beneficial effects will be maintained after 12 months.
- Reading measures correlate with cortical thickness (CT) in the visual cortex;

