To subjectively assess reading effort, we will administer a reading habit questionnaire, a measure developed specifically to evaluate the extent and frequency to which an individual engages in reading activities during their activities of daily living, including reading for entertainment or education. This measure has previously been employed by our team³⁹ and includes questions on language background (e.g., mother tongue, language proficiency), assessed self-reported proficiency in reading (1=no ability, 5=fluent ability), and reading habits before and after onset of low vision (e.g., frequency, enjoyment, type of reading). In addition, participants will be asked to read English or French paragraphs from the

International Reading Speed Test (IReST)⁷⁷. It includes reading comprehension questions that have previously been developed and used in our lab in the context of a low vision reading evaluation using the iPad as a magnification device³⁹. They will also read the English or French version of the MNRead chart⁷⁸, a clinical assessment chart that allows for the measurement of reading acuity (smallest print read), reading speed (in words per minute), critical print size (smallest print at which reading speed is still optimal), and the Reading Accessibility Index⁷⁹, which considers reading ability over a range of print sizes. Finally, we administer a primed lexical decision task where the participant first reads a sentence (prime) and then decides on a word (target) as quickly and as accurately as possible. This task evaluates reading speed, vocabulary comprehension and ability to judge content congruency^{80,81}.

Measures of Participant Characteristics

Depression, Anxiety, Stress: Not surprisingly, the onset of age-related vision loss due to AMD is often accompanied with a multitude of emotional responses that can potentially interfere with the success of low vision rehabilitation. Therefore, the Depression, Anxiety and Stress Scale⁸² will be included in the protocol in order to identify individuals whose rehabilitation outcomes might be influenced by their psychological state. This 21-item questionnaire shows exquisite psychometric properties and has been validated in both English and French⁸³.

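### The self-report measure of reading effort is a questionnaire on how much people read, so effort and reading behaviour are not separated; separately, reading speed is given the wrong direction in Hypothesis 1

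*Combined protocol and SAP*

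**What the plan says.** The hypotheses are not numbered in the protocol; they are numbered here in the order listed.

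- **Hypothesis 1:** "Measures of reading effort (self-report and objective reading speed) will be statistically significantly reduced" once participants have received reading strategies and tools.
- **Hypothesis 2:** "Measures of reading behaviour will be negatively correlated with measures of reading effort". The example given is that "participants who report less effort will read a greater amount, more frequently and for longer".
- **Hypothesis 3:** people with reduced effort and improved reading behaviour will improve on cognitive tests, compared with those whose effort stays high or whose behaviour does not change.
- **Reading Outcome Measures, subjective effort:** "To subjectively assess reading effort, we will administer a reading habit questionnaire". The same sentence calls it "a measure developed specifically to evaluate the extent and frequency to which an individual engages in reading activities". The content listed is language background, "assessed self-reported proficiency in reading (1=no ability, 5=fluent ability", and "reading habits before and after onset of low vision (e.g., frequency, enjoyment, type of reading".
- **Reading Outcome Measures, objective tests:** IReST paragraphs, the MNRead chart (speed in words per minute) and a primed lexical decision task.
- **Statistical Analysis – Functional measures:** mixed-effects models of change in cognitive scores, compared across sensory groups. Reading effort and reading activity enter under the exploratory analyses.

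**The concern.** Hypothesis 3 describes a chain: reading becomes less effortful, people read more, and cognition benefits. To examine it, effort and behaviour must be two separately scored quantities. The only instrument named for subjective effort is described in terms of behaviour, and no other instrument is named for behaviour. A self-report association between the two could then reflect shared questionnaire content and not a relation between effort and reading.

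The second problem is one of sign. Reading speed is listed as an effort measure that should fall, yet successful rehabilitation should raise it. The Study Design section says the design and analysis will be submitted as a stage 1 pre-registered report, where each measure and its predicted direction should be unambiguous.

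**Working it through.** The check is mainly a comparison of passages.

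**1. Effort against behaviour.** Hypothesis 2 explains behaviour as amount, frequency and duration of reading. The questionnaire is said to evaluate "the extent and frequency to which an individual engages in reading activities". Extent and frequency therefore appear on both sides. Of the other listed content, language background is not effort, proficiency is a self-rating of ability, and enjoyment and type of reading are habits. The section on why low vision makes reading effortful treats effort as cognitive resources diverted to meet the demands of the task. No listed item asks about that, and no scoring rule derives an effort score.

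**2. Consequence for a self-report correlation.** Write the effort score as E = S + e and the behaviour score as B = S + b, where S is shared item content and e and b are uncorrelated with S and with each other. Then

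corr(E, B) = var(S) / √[var(E) · var(B)],

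which is above zero even though e and b are unrelated. If E is reverse-scored, the sign flips. In the limit of identical items the correlation is +1, or −1 after reversal. Scoring would thus settle part of the result that Hypothesis 2 is meant to test. No value can be entered for var(S), because the documents give neither the full item list nor the scoring.

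**3. Consequence for Hypothesis 3 and exploratory analysis 1.** Both classify people by effort going down and reading going up. If effort were an unreversed frequency score, the two conditions would contradict each other. If it were a reversed frequency score, they would be one condition stated twice.

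**4. Direction of reading speed.** Four places treat higher speed as better:
- central vision loss is said to lower reading speed (section on effortful reading);
- raising speed at smaller print is described as a frequent main target of rehabilitation (section on rehabilitation and reading effort);
- faster readers had better MoCA scores in the pilot data (text before the objectives);
- MNRead speed is in words per minute, so a higher value is faster (Reading Outcome Measures).

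Hypothesis 1 alone lists speed among the things to be reduced. Hypothesis 2's negative sign has the same problem if speed is entered unreversed. No reverse coding is specified.

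**5. What is not touched.** The Sample Size section gives n = 141 for a 3x3 within-between design, effect size 0.15, alpha 0.05 and power 0.95. Reading 0.15 as Cohen's f, and assuming a correlation of 0.5 between repeated measures and no sphericity correction (neither is stated), the group-by-time interaction has

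λ = f²·N·m/(1 − ρ) = 0.0225 × 141 × 3 / 0.5 = 19.04, with df = 4 and (141 − 3) × 2 = 276.

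Power is 0.952. The smallest N is 140, or 141 with three equal groups, so the figure reproduces. No effort score enters this calculation or the main model of cognitive scores.

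**The case against.** The strongest reply has four parts.

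- **The intent on speed is plain.** The subject of Hypothesis 1 is effort, and speed is its indicator. This stands. A reader might infer that the plan predicts slower reading, but the rest of the protocol rules that out. It is an error of wording.
- **Hypothesis 2 has a clean route.** IReST or MNRead speed can be correlated with reported reading frequency, and these come from different instruments. This also stands. A reader might conclude that Hypotheses 1 and 2 cannot be tested at all, but that goes too far: the overlap affects only the self-report part.
- **The questionnaire cannot be seen.** The protocol says what it includes, gives examples and cites earlier use, so the list is not exhaustive. The proficiency rating is also distinct from the frequency questions. One may therefore say that no effort item is identified, but not that none exists. Even so, a plan that names the instrument as its effort measure should say which items score effort.
- **The reach is limited.** The main model does not use an effort score, and where a reading measure is only a covariate (exploratory analysis 2), reversing its sign does not change the adjustment. This stands and limits the point to the hypotheses about mechanism.

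The reply leaves the self-report problem unanswered. Changing a sign does not turn a frequency score into an effort score.

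**Conclusion.** The point holds in a limited form. As written, the self-report parts of Hypotheses 1 and 2, and the effort/behaviour classification in Hypothesis 3 and exploratory analysis 1, rest on one questionnaire for two constructs. A change in its extent and frequency score would show a change in how much people read, not in how hard reading is. A self-report correlation would be partly built in.

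The direction given for reading speed in Hypothesis 1 is a separate wording error. Once it is corrected, the speed-based tests are sound.

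The size of the built-in correlation cannot be given, since any figure would rest on an assumed overlap for which the documents offer no basis. A reader might also infer that the cognitive comparison between groups or the sample size is compromised. Neither is, because neither uses an effort score. The conclusion assumes that the items described in Reading Outcome Measures are representative of the questionnaire. If it contains separate effort items, naming them would resolve the self-report part.

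**What to change.** 1. Assign the questionnaire's extent and frequency items to reading behaviour only, and state how that score is formed.
2. Use IReST and MNRead speed, both already planned, as the objective effort indicator, with one coding throughout: words per minute. Restate Hypothesis 1 so that speed is predicted to increase after rehabilitation, and Hypothesis 2 so that speed correlates positively with reading behaviour.
3. For subjective effort, either name existing questionnaire items that ask about effort and do not contribute to the behaviour score, or drop the self-report effort claim from Hypotheses 1 to 3.
4. Optionally, add a brief self-rated effort item after the IReST reading at each visit.
5. Carry the same definitions into exploratory analysis 1 and the pre-registered report.

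Items 1, 2, 3 and 5 change wording only. Item 4 adds a short rating at each visit, and the documents offer no validation for such an item, so it should be presented as supplementary.

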Cognitive Outcome Measures: We will investigate the potential effect of reading rehabilitation on three relevant areas of cognitive function. The first will be episodic learning and memory, assessed using the Rey Auditory Verbal Learning Test (RAVLT)⁶⁹. Second, we will assess two aspects of auditory working memory: a) general auditory working memory and will be assessed using the WAIS-IV Letter Number Sequencing task⁷⁰ and b) an auditory listening span test, which will be a variant of the reading span task originally developed by Daneman and Carpenter⁷¹ (a task highly associated with reading skill). The third domain is processing speed, and will be assessed using a computerized audio-visual choice reaction time task. Lastly, we will be assessing cognitive impairment using the adapted version of the Montreal Cognitive Assessment (MoCA)^{59,72} for persons with visual impairment, should their visual impairment be too severe to administer the visual items. This measure will provide additional information regarding the participants' cognitive abilities, and help to identify possible cognitive impairment. These measures were chosen because they cover a wide range of cognitive functions, they are all **administered in the auditory domain** and thus will not be affected by a visual impairment, and have good psychometric properties. In other words, should performance on these cognitive measures improve following the vision rehabilitation program, the improvement will be attributable to the benefit of increased visual function on cognitive stimulation as opposed to merely being due to improved perception of the stimuli involved in the tests. Their administration can be **adjusted to make instructions audible** for persons with concurrent hearing loss. Moreover, they assess cognitive domains that have been shown to predict everyday function in older adults: episodic learning and memory⁷³, processing speed⁷⁴, and working memory⁷⁵. In addition, we have aimed to harmonize as many of our cognitive measures as possible with those utilized in the Canadian Longitudinal Study on Aging, in order to increase the possibilities to compare our findings to that larger data set for 30,000 Canadians for whom baseline and first follow-up data are available⁷⁶.

Reading Outcome Measures:

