Hearing Assessment: Given that the cognitive assessment is designed in such a way that vision is not required for the administration of the testing materials, and given that the influence of **hearing** loss has been associated with the measurement of cognition^{e.g., 84} and has been identified as a risk factor for cognitive impairment²⁴, hearing ability will be assessed as part of the protocol. In order to be able to consider hearing ability and listening effort during the cognitive assessment²⁹, participants will complete a pure-tone audiogram with a portable audiometer (Maico MA41 from GénieAudio), using Radioear DD45 earphones, to establish a mean unaided decibel hearing loss (dB HL) threshold across 0.5, 1, 2, and 4 kHz in each ear. We will document the ambient sound levels during testing, using the Decibel X app by SkyPaw Co. Ltd., because testing may be conducted in participants' homes. Ambient noise levels can then be used to statistically control for potential noise effects on hearing thresholds. For individuals who experience difficulties in hearing the experimental protocol instructions, we will have a Williams Sound Pocketalker (<https://www.williamsound.com/pocketalker>) on site in order to provide personalized amplification. In addition to pure-tone audiometric thresholds, speech-in-noise thresholds will be measured using the Canadian Digit Triplet Test in either English or French⁸⁵. Participants will complete the Hearing Handicap Inventory for the Elderly (HHIE) questionnaire and three individual questions about hearing ability which assesses their perception of difficulties with activities of daily living that require hearing⁸⁶. These hearing assessments are the same as those that have been used or are planned for the Canadian Longitudinal Study on Aging (CLSA)⁸⁷, thereby allowing us to cross-reference and compare data from both studies and optimize our ability to place our intervention findings in a larger Canadian context.

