Sample Size: Effect sizes in vision rehabilitation in the past have ranged from approximately Cohen's $d = .20$ to 2.5 ³⁸. Since there are no existing effect size estimates for cognitive ability in the context of low vision rehabilitation, we are applying these values as a guide line: Using an average value of $d = 1.0$, and converting this value into variance accounted for ($r^2 = .20$ ¹⁰⁵), we can estimate a required sample size. Using a 3x3 (group x time point) within-between design for Analysis of Variance, power analysis using gPower¹⁰⁶ indicates that a sample size of $n = 141$ allows us to detect small effect sizes of .15 or greater, with an alpha of 0.05 and a desired power of .95. We expected an attrition rate of around 10% at each time point, given our previous research with older visually impaired adults^{107,108}. Therefore, a sample of $n = 200$ (to yield 150 patients, 50 controls) should be sufficient for our protocol. This goal is feasible given an average of 3000 new referrals to rehabilitation in Montreal per year.

Data Collection

Time 1 – Pre-Reading Rehabilitation: Participants will complete the questionnaires, hearing, reading and cognitive assessment components between their initial global intake exam and their first rehabilitation appointment. This period can span anywhere around 3 months, depending on waiting lists, and we will track whether any substantial changes in health occurred during this period that could influence eligibility or data collection.

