Time 2 – 6-Months and Time 3 – 12-Months Follow-Up: Six and 12 months after the initial rehabilitation appointment, the research assistant will meet with each participant (at home or in the lab, according to their preference) in order to repeat the experimental protocol, and all reading, cognitive and hearing measures will be administered each time. Throughout the period of the protocol, data from the rehabilitation chart will be extracted as it becomes available, with the final data collection concluding after the 12-month follow-up.

Statistical Analysis – Functional measures: To analyze these data, we will examine change in cognitive test scores from baseline over time using mixed-effects regression models, adjusting for level of vision and hearing impairment as fixed or random effects, and compare across sensory group (VI/DSI/Control). The analyses will include consideration of potential moderators or confounders (i.e., gender, age, education). In addition, we will calculate effect sizes, confidence intervals and Bayes Factors for main effects, interactions, and all post-hoc analysis.

When reflecting on the question of a control group we further consulted with the rehabilitation centres and discussed recruitment approaches and limitations; however, for practical and ethical reasons we are not able to withhold rehabilitation services from a possible comparison group, and waiting times are too varied across the centers and seasons of the year to allow for a waiting-list control group. As a result, we are proposing a quasi-experimental repeated-measures design with the intent to let the participants act as their own comparison across time points.

In addition, the data allow us to follow potential **exploratory avenues of analysis:**

- 1) If the recruited participants naturally divide into individuals whose reading effort was reduced and their reading activity has increased, versus those where we do not observe a change in reading behaviour, we can compare these two groups directly (e.g., while still considering their hearing status, or their gender)

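### The memory and working-memory outcomes are heard tests, but amplification and test location may change between visits and the cognitive model has no term for either, so a change in audibility can be read as a change in cognition

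*Combined protocol and SAP*

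**What the plan says.** Under Cognitive Outcome Measures, episodic memory is tested with the RAVLT and working memory with Letter Number Sequencing and an auditory listening span. The section stresses that the cognitive measures are given by ear. It argues that a gain after rehabilitation would reflect better visual function feeding cognition, "as opposed to merely being due to improved perception of the stimuli involved in the tests". It adds that administration can be adjusted so that people with hearing loss can hear the instructions.

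Under Hearing Assessment, "For individuals who experience difficulties in hearing the experimental protocol instructions", the plan says "we will have a Williams Sound Pocketalker" on site. Sound level is documented during testing because testing may take place at home, and "Ambient noise levels can then be used to statistically control for potential noise effects on hearing thresholds". The pure-tone average is unaided. A speech-in-noise test is also given, and the section's stated aim is to take hearing and listening effort into account in the cognitive assessment.

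Under Participants, the first session may be at home or in the lab. At 6 and 12 months the visit is again "at home or in the lab, according to their preference", and the reading, cognitive and hearing measures are all repeated.

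Under Statistical Analysis – Functional measures, change in cognitive scores is modelled by mixed-effects regression, adjusted for level of vision and hearing impairment and compared across VI, DSI and control groups. No term is named for amplification, location or noise. The same section explains that no untreated low-vision group is possible and that participants serve as their own comparison over time.

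**The concern.** In a non-randomised before-and-after design, the comparison over time is only as good as the constancy of the test conditions. Here three conditions that affect how well a spoken list is heard can differ between Time 1 and later visits: whether an amplifier is worn, where the test is done, and how noisy it is.

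The protocol itself supplies the mechanism. Its background on effortful listening says that hearing loss or noise draws off cognitive resources and leaves less for understanding and remembering speech. On that account, someone tested without amplification at Time 1 and with it at Time 2 could score higher with no change in cognition, and the reverse change could lower the score.

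The DSI group is the likeliest to be affected, because its entry criterion is an unaided loss of 26 to 70 dB. Controls have age-normal hearing, so their change over time would not cancel a shift in the DSI group. At stake is the second research question, whether any benefit is equally strong in VI and DSI, and also the within-group change in DSI.

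**Working it through.** **Passages side by side**

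| Condition | What may vary | Safeguard stated | What the safeguard leaves open |
|---|---|---|---|
| Amplification | Offered when instructions are hard to hear; no setting, record or carry-forward; own hearing aids not mentioned | Hearing retested each visit; model adjusts for hearing level | Thresholds are unaided, so they do not show amplifier or aid use during the cognitive tests |
| Location | Home or lab, chosen at each visit | None stated | Not in the model |
| Ambient noise | Varies with place and day | Sound level documented | Stated use is for hearing thresholds; not assigned to cognitive scores |

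The argument about perception of the stimuli follows from giving the tests by ear. That closes the visual route and leaves the auditory route open.

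**The plan's own figure.** The Sample Size section gives n = 141: "Using a 3x3 (group x time point) within-between design for Analysis of Variance", which "allows us to detect small effect sizes of .15 or greater, with an alpha of 0.05 and a desired power of .95". For the group-by-time interaction, with 3 groups, 3 times, and correlation 0.5 and sphericity assumed (neither is stated):
- λ = f² × N × 3 / (1 − ρ) = 0.0225 × 141 × 3 / 0.5 = 19.04
- df = 4 and (141 − 3) × 2 = 276; power = 0.952
- the smallest N is 140, which rounds up to 141 for equal groups

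The stated figure reproduces, and this point does not change it. The correlation of 0.5 that it needs is carried forward below.

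**Sensitivity of the DSI v VI comparison.** The documents give no audibility effect, so this is a range under assumptions.
- Patients: 150 (Sample Size). Split 75/75: assumed.
- Attrition: "We expected an attrition rate of around 10% at each time point". Over two follow-ups, 75 × 0.9 × 0.9 = 60.75, about 61 per group at 12 months.
- SD of change = √(2 × (1 − 0.5)) = 1 baseline SD.
- SE of the DSI − VI difference in change = √(2/61) = 0.181 SD.
- Net DSI shift = net share whose audibility improves × gain per person. Assumed 20% × 0.3 SD = 0.06 SD, up to 30% × 0.5 SD = 0.15 SD. Zero is included because nothing in the documents excludes it.
- Two-sided rejection rate with no true effect and no shift in VI = Φ(d/SE − 1.96) + Φ(−d/SE − 1.96).

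| Net DSI shift d | d/SE | False-positive rate |
|---|---|---|
| 0 | 0 | 5.0% |
| 0.06 SD | 0.33 | 6.3% |
| 0.10 SD | 0.55 | 8.6% |
| 0.15 SD | 0.83 | 13.2% |

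Group size alters this modestly. At a shift of 0.10 SD the rate is 7.7% with 47 per group and 9.4% with 75 per group. For change within DSI alone, SE = 1/√61 = 0.128, and shifts of 0.06 to 0.15 SD give 7.6% to 21.6%.

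**Balanced changes.** If 20% change condition by 0.5 SD, equally up and down, the mean shift is zero. The variance of change rises by a factor of 1 + 0.2 × 0.5² = 1.05, and the false-positive rate stays at about 5%.

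**The case against.** The strongest reply is that the plan permits these changes but does not say they will happen or in which direction. The amplifier is available from Time 1, so a person who struggles then would be offered it then. Location and noise can move either way in any group. A reader might infer that the bias favours apparent benefit. The documents do not support that: it needs a net move from unamplified to amplified after baseline, and no section implies one. If DSI participants in truth benefit less, an upward shift would hide the VI–DSI difference rather than create one. This objection stands in full as to size and direction.

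A reader might also infer that hearing is ignored in the outcome analysis. It is not. Hearing is measured at each visit, including speech in noise, and the cognitive model adjusts for hearing level. The noise sentence is permissive, so using noise in the cognitive model is not ruled out. Nor does the plan expressly claim to have excluded an auditory explanation. In context, its statement about perception answers the visual route, and hearing is handled in a separate sentence about instructions. These safeguards reduce the problem, but they do not record the listening condition under which each score was obtained.

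Finally, a strict freeze of the Time 1 condition could bias results the other way if hearing worsens over 12 months. Amplifier use as a covariate in the main model would be confounded by the reason for using it. Both points are accepted and shape the fix.

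**Conclusion.** The gap is real: the plan neither holds constant nor records amplification, does not hold location constant across visits, and assigns none of amplification, location or noise to the cognitive model. It is a threat to interpretation of unknown size and direction, not a demonstrated bias. Under the stated assumptions, the DSI v VI false-positive rate lies between 5% (no net shift, or balanced changes) and 13% (net shift of 0.15 SD). The 75/75 split, the correlation, the share changing condition and the gain per person are assumptions, not figures from the documents. That DSI is the group most affected is an inference from its entry criterion; noise and location could affect every group. The change is worth making because it is cheap and because unrecorded amplifier use cannot be recovered later.

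**What to change.** 1. Decide each participant's audibility support at Time 1 and apply it to the test stimuli as well as the instructions.
2. By default, repeat the same listening condition and location at Times 2 and 3. Allow documented changes if hearing changes or the participant prefers another place.
3. At every cognitive session, record amplifier or own-aid use, the setting and the location.
4. Enter the ambient noise already being measured, and the location, as visit-level covariates in the cognitive models. Keep amplifier use out of the main model.
5. Report a sensitivity analysis for participants whose listening condition changed, noting that such changes may reflect worsening hearing.
6. Limit the statement in Cognitive Outcome Measures about improved perception of the stimuli to visual perception.

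The cost is a line on the test form, a few model terms and one further analysis. That analysis selects on a post-baseline event, so it supports the main result and does not replace it. Location remains the participant's choice, and no extra visits or participants are needed.
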